7.0 EVALUATIONS/MATERIAL AND DATA TO BE ACCESSIONED

Timing of protocol therapy administration, response assessment studies, and surgical interventions are based on schedules derived from the experimental design or on established standards of care. Minor unavoidable departures (up to 72 hours) from protocol directed therapy and/or disease evaluations (and up to 1 week for surgery) for valid clinical, patient and family logistical, or facility, procedure and/or anesthesia scheduling issues are acceptable (except where explicitly prohibited within the protocol).

7.1 End of Therapy & Follow-up

See COG Late Effects Guidelines for recommended post treatment follow-up:
<http://www.survivorshipguidelines.org/>.

NOTE: Follow-up data are expected to be submitted per the Case Report Forms (CRFs) schedule.

STUDIES TO BE OBTAINED	End of Therapy	At Relapse
Physical Exam	X	
Ht, Wt	X	
Performance Status	X	
CBC, differential, platelets	X	
Electrolytes including Ca ⁺⁺ , PO ₄ , Mg ⁺⁺	X	
AST, ALT, albumin	X	
TSH	X	
Urinalysis	X	
Urine Protein/Creatinine	X	
ECG	X	
MUGA or ECHO	X	
Creatinine, bilirubin	X	
GFR or Creatinine Clearance	X	
Tumor Imaging	X	X
Immune Biomarkers in Blood (for consenting patients; see Section 15.2.1)	X	
Immune Biomarkers in Tissue (for consenting patients; see Section 15.2.2)		X*
Specimens for Banking (for consenting patients; see Section 15.2.3)		X*

* if available

7.2 Follow-up Studies to be Obtained

Patients must have follow-up assessments after completion of protocol therapy for a minimum of 4 years. Follow-up at year 5 and beyond is at the discretion of the treating physician.

History/Physical Exam, CBC (if clinically indicated), Electrolytes, creatinine, tumor imaging, and other studies as required for good patient care.

- Year 1 (Months 3, 6, 9, 12)

- Year 2 (Months 16, 20 and 24)
- Year 3 (Months 30 and 36)
- Year 4 (Months 42 and 48)

7.3 Research Studies for which Patient Participation is Optional

1. Immune biomarkers in blood (see [Section 15.2.1](#)) will be collected at:
 - Baseline, Day 1 of Cycles 2, 3, and 9 (within 72 hours prior to Day 1 dosing), and within 3 weeks after the last dose of study treatment.
2. Immune biomarkers in tumor tissue (see [Section 15.2.2](#)) will be collected at:
 - Baseline (if available), and at any time tumor tissue is obtained (i.e., surgery, relapse).
3. Specimens for Banking (see [Section 15.2.3](#)) will be collected at:
 - Baseline (if available), and at any time tumor tissue is obtained (i.e., surgery, relapse) for tumor tissue. Prior to any chemotherapy for whole blood, serum and urine specimens.

8.0 CRITERIA FOR REMOVAL FROM PROTOCOL THERAPY AND OFF STUDY CRITERIA

8.1 Criteria for Removal from Protocol Therapy

- a) For Arms A and C, progressive disease of $\geq 40\%$ increase in total tumor burden from baseline or nadir at any time during protocol therapy (see [Section 10.2](#)) (see exception below).
- b) For Arms A and C, progressive disease of $\geq 20\%$ increase in total tumor burden from baseline or nadir that occurs > 12 weeks after start of protocol therapy, except if a patient met the criteria for pseudoprogression in the first 12 weeks and the total tumor burden has subsequently stabilized or decreased with no additional growth (see [Section 10.2](#)) (see exception below).
- c) For Arm B, progressive disease of $\geq 20\%$ increase from baseline or nadir in total tumor burden at any time during protocol therapy (see [Section 10.2](#)).
- d) Response followed by $\geq 20\%$ increase in total tumor burden from the nadir at any time during protocol therapy (see [Section 10.2.5.1](#)) (see exception below).
- e) Appearance of one or more new lesions or unequivocal progression of non-target lesions (see [Section 10.2.5.2](#)) and refer to [Section 10.2.1](#) for exceptions within the first 12 weeks of therapy (see exception below).
- f) Resection of any malignant lesion within the first 12 weeks of protocol therapy (see [Section 13.1.8.1](#)).
- g) Resection of any lesion that is increasing in size at any time while on protocol therapy (see [Section 13.1.8.2](#)).
- h) Completion of planned therapy.
- i) Unacceptable toxicity due to protocol therapy (see [Section 5.0](#)).
- j) Refusal of further protocol therapy by patient/parent/guardian.
- k) Physician determines it is in patient's best interest.
- l) Development of a second malignancy.
- m) Pregnancy.
- n) Repeat eligibility studies (if required) are outside the parameters required for eligibility (see [Section 3.2](#)).

Exception: Patients on Arm C who meet the protocol defined criteria of disease progression prior to Cycle 22 of therapy, may cross-over and receive the remainder of their protocol therapy per Arm A. For those patients who cross-over, the total protocol therapy received on AREN1721 is not to exceed 26 cycles or 2 years, whichever comes first.

Important Note: *For criteria (a)-(c) above, calculations of percentage change in total tumor burden should fully exclude from consideration any malignant lesions that were surgically resected at any time prior to the most recent response assessment. See [Section 10.2](#) for details.*

Patients who are off protocol therapy are to be followed until they meet the criteria for Off Study (see below). Follow-up data will be required unless patient is taken off study.

8.2 Off Study Criteria

- a) Death.
- b) Lost to follow-up.
- c) Patient enrollment onto another COG study with tumor therapeutic intent (e.g., at recurrence).
- d) Withdrawal of consent for any further data submission.
- e) The fifth anniversary of the date the patient was enrolled on this study.

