3.0 STUDY ENROLLMENT PROCEDURES AND PATIENT ELIGIBILITY

3.1 Study Enrollment

3.1.1 Patient Registration

Prior to enrollment on this study, patients must be assigned a COG patient ID number. This number is obtained via the Patient Registry module in OPEN once authorization for the release of protected health information (PHI) has been obtained. The COG patient ID number is used to identify the patient in all future interactions with COG. If you have problems with the registration, please refer to the online help. For additional help or information, please contact the CTSU Help Desk at [name] or [contact].

A Biopathology Center (BPC) number will be assigned as part of the registration process. Each patient will be assigned only one BPC number per COG Patient ID.

For additional information about the labeling of specimens please refer to the Pathology and/or Biology Guidelines in this protocol.

Please see [Appendix I](#) for detailed CTEP Registration Procedures for Investigators and Associates, and Cancer Trials Support Unit (CTSU) Registration Procedures including: how to download site registration documents; requirements for site registration, submission of regulatory documents and how to check your site's registration status.

NOTE: In order for an institution to maintain COG membership requirements, every patient with a known or suspected neoplasm needs to be offered participation in APEC14B1, *Project: Every Child A Registry, Eligibility Screening, Biology and Outcome Study*.

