9.0 STATISTICAL CONSIDERATIONS

9.1 Sample Size and Study Duration

As of Amendment 5A, which now allows crossover upon progression from the nivolumab arm to the nivolumab + axitinib arm, we expect enrollment of approximately 2 patients per month. This is derived from tRCC prevalence, access to treatment centers, and enrollment patterns to date, which should be aided by the crossover.

To reduce the overall sample size from the prior design, we have maintained the same overall study design but changed two design parameters: 1-sided alpha will be increased from 0.05 to 0.15, and the targeted hazard ratio will be reduced from $HR = 0.50$ to $HR = 0.40$. With these changes, 22 PFS events will be required to address the primary objective comparing Arms A and C at the time of final analysis (see [Section 9.2](#)). Allowing that approximately 25% of eligible and evaluable patients may not have experienced a PFS event by the time of the final analysis, the target accrual on this study is 28 patients. To account for an additional estimated 5% of patients who might be found to be ineligible for the study or inevaluable for the primary endpoint at the time of or following study enrollment (e.g., due to randomization to Arm B, no central path review performed, or having central path review confirming a diagnosis other than tRCC), the ceiling accrual will be set to 40 patients, including those patients already enrolled.

If the study accrues to the target accrual without interim stopping for futility, the additional time required to enroll up to this maximum once re-opening under Amendment 5A is estimated to be 14 months. As before, all eligible patients will be followed for 5 years after randomization, and the final analysis will be conducted once the target number of PFS events needed for the final analysis has been reached, or after 2 years of follow-up is obtained for the last patient enrolled, whichever occurs first.

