9.3 Methods of Analysis

Primary Endpoint Analyses

The primary endpoint, progression-free survival, is formally defined in [Section 9.4](#) below. Due to the small size of this trial and the need to preserve alpha-spending for the final analysis, there will be no formal interim analyses of PFS for early efficacy, though this trial will be periodically reviewed by the COG DSMC.

Prospective formal interim analyses for futility will be performed once 50% (11) of the 22 targeted PFS events have been observed. The trial will stop early for futility if, given the data observed to date, the observed hazard ratio for PFS is greater than 1.00, suggesting a trend toward worse outcomes for Arm A (nivolumab + axitinib) compared to Arm C (nivolumab alone).

The final PFS analysis will be performed based on the first quarterly data freeze where at least one of the following criteria are met: (1) a minimum of 2 years of follow-up has been obtained for each patient still “at risk” for a PFS event or (2) when at least 22 PFS events needed for a fully powered final analysis have been confirmed. At this time, a stratified, one-sided log-rank test (using the stratification factors at randomization, age and prior therapy, if stratum-specific sample sizes allow) will be performed to compare treatment arms with alpha = 0.15. A stratified Cox proportional hazards model will also be fit to evaluate the final hazard ratio between the treatment arms (stratification as numbers allow); this will be reported with a 70% confidence interval (to align with the overall alpha level of the primary log-rank test).

While post-progression outcomes on combination therapy among patients who receive crossover upon first progression on the nivolumab-only arm (Arm C) will not be counted toward the primary endpoint analyses, their post-progression experience, including time from first progression to second progression or death (second PFS) will be summarized descriptively.

Secondary Endpoint Analyses

Secondary endpoints OS and ORR (defined in [Section 9.4](#) below) as well as all Grade 3 non-hematologic adverse events and all Grade 4 and higher adverse events will be monitored for data cleanliness and routine reporting as well as formally compared at the time of the final analysis for the primary endpoint, as described below. For ORR and OS below, stratifications factors again may be collapsed and/or omitted depending on the final counts.

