ORR: A logistic regression model for overall response, stratified by the stratification factors used at randomization (age and prior therapy) will be fit, including treatment arm as a key covariate. From this model, the odds ratio for treatment arm will be reported with a 70% confidence interval. The ORR observed within each treatment arm will also be reported.

OS: A stratified, one-sided log-rank test (using the stratification factors at randomization, age and prior therapy) will be performed to compare treatment arms with alpha = 0.15. Cox proportional hazards models will also be fit to evaluate the final hazard ratio between the treatment arms, with exploratory modeling taking into account the potential influence of other factors (e.g., baseline disease burden, upfront vs. delayed nephrectomy). From these models, the hazard ratio for treatment assignment will be reported with a 70% confidence interval (to align with the overall alpha level of the primary log-rank test).

AEs: All Grade 3 or higher non-hematologic toxicities and all Grade 4-5 adverse events occurring during protocol therapy or within 100 days of treatment discontinuation, including crossover for patients who receive crossover combination therapy, will be analyzed. The rates of these events will be reported separately by treatment arm (including crossover as a “3rd” arm for this purpose), and both by individual AE and class of AE (e.g., hematologic). Given that some AEs may be rare, Fisher Exact tests will be used to test for statistical significance among any apparent differences by treatment arm.

Exploratory Analyses

Exploratory Aim 1.3.1: To characterize tRCC clinical behavior across all age groups.
We will list and summarize the frequency of site(s) of disease at presentation (including extent of lymph node involvement), site(s) of relapse, surgical practices on protocol therapy, and radiotherapy practices on protocol therapy. We will also summarize the overall response rate (ORR) submitted by the enrolling institution.

Exploratory Aim 1.3.2: To evaluate type of antitumor immune response and stability of T cell activation before and after treatment with immunotherapy or antiangiogenic therapy.

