9.4 Endpoints and Evaluability

The primary endpoint is progression-free survival (PFS), which is defined as the time from randomization to the earliest occurrence of disease progression (as defined by modified RECIST criteria for immunotherapy, described in [Section 10](#)) or death due to any cause among patients who initiated protocol treatment. Patients not experiencing a PFS event by the time of a prospectively-planned interim or final analysis will be right-censored at the time of their most recent response/progression evaluation. Following the intent-to-treat principle, all patients who are randomized and confirmed to have tRCC by central pathology review will be evaluable for PFS. Patients randomized to Arm B prior to Amendment 2A, and patients who have a central path review confirming a diagnosis other than tRCC, or who never receive central path review per protocol, will be considered inevaluable for the primary endpoint comparison but included in study descriptive statistics.

The overall response rate (ORR) will be defined as the rate of complete or partial responses (assessed by imaging) among patients who initiated protocol therapy and completed at least one subsequent imaging assessment. Patients who are randomized to Arms A or C and are confirmed to have tRCC by central pathology review will be evaluable for ORR.

Overall survival (OS) will be calculated as the time from randomization to death due to any cause, with surviving patients being right-censored at their length of follow-up at the time of analysis. Patients who are randomized to Arms A or C and are confirmed to have tRCC by central pathology review will be evaluable for OS.

Note: For calculations of both PFS and ORR, any lesions resected during protocol therapy for reasons other than progression (as noted by sites or documented upon central surgical review) will not contribute toward response/progression assessments. Response/progression assessments are scheduled to take place after Cycles 2, 4, 6, 9, 12, and then every 4 cycles thereafter, after every cycle following any suspected pseudoprogression until the total tumor burden subsequently diminishes, or at any time clinical progression is suspected. Once in follow-up, patients without a documented PFS event will be evaluated according to the schedule in [Section 7.2](#). ORR and OS will be analyzed as a part of exploratory aim 1.3.1.

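### Section 8.2(c) stops survival follow-up when a patient joins another COG therapeutic study, against the five years promised in 9.1, so the tested OS comparison may be informatively censored

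*Combined protocol and SAP*

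**What the plan says.** Section 8.2(c) of the combined protocol and SAP lists "Patient enrollment onto another COG study with tumor therapeutic intent (e.g., at recurrence" among the events that take a patient off study. Section 8.1 links follow-up to that list: "Patients who are off protocol therapy are to be followed until they meet the criteria for Off Study", and "Follow-up data will be required unless patient is taken off study". After an 8.2(c) exit, therefore, no further data are required.

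Section 9.1 says that "all eligible patients will be followed for 5 years after randomization" and names no exception.

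Section 9.4 defines OS from randomization to death, "with surviving patients being right-censored at their length of follow-up at the time of analysis". It has no rule for patients who leave under 8.2(c). Section 9.3 lists OS as a secondary endpoint, "formally compared at the time of the final analysis for the primary endpoint", using a stratified one-sided log-rank test that "will be performed to compare treatment arms with alpha = 0.15". Section 9.4 nevertheless assigns OS to exploratory aim 1.3.1.

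Sections 4.1, 4.5.3 and 8.1 let Arm C patients who progress before Cycle 22 cross over and remain on protocol therapy. Arm A patients who progress come off protocol therapy.

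**The concern.** Log-rank and Cox analyses of OS assume that a censored patient has the same future risk of death as comparable patients still followed. An exit whose own example is recurrence puts that in doubt. It removes patients who have progressed, at the point where risk rises, and leaves behind a set enriched with patients who have not progressed.

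If the exit falls at a different point in the disease course in each arm, the OS hazard ratio can shift with no true difference. Crossover creates that possibility. An Arm A patient is free to join another study at first progression, while an Arm C patient who crosses over would normally do so only at second progression. With few deaths expected at the OS test, losing one or two matters.

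**Working it through.** **1. The texts side by side.** Section 9.1 requires five years for everyone eligible. Sections 8.1 and 8.2(c) end data collection earlier for a defined group. Nothing elsewhere continues vital status after that exit, and no sensitivity analysis is planned. The conflict stands without any calculation.

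**2. The plan's own figures.** There is no OS power, OS event target or exit rate to reproduce. The nearest figures are the PFS operating characteristics in 9.2, which matter here because the futility stop decides whether a final OS test happens. The Freedman drift is √d·(1−HR)/(1+HR).
- HR 0.40 at 11 events: 3.317 × 0.4286 = 1.42, so the chance of stopping is 7.8% (stated 8%).
- HR 0.40 at 22 events: 4.690 × 0.4286 = 2.01. Against a critical value of 1.036, and allowing for the futility look (correlation √0.5), power is 81.0% (stated 80%).
- HR 1.0: 50% stop and 13.9% reach significance (stated 50% and 14%).

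**3. Size under Model 1 (inputs assumed unless noted).** The model has 14 patients per arm (28 in 9.2), uniform accrual over 14 months (9.1) and analysis at the 22nd PFS event (9.2). Arm C median PFS is 6 months. Median post-progression survival is 12 months in both arms. Crossed-over patients reach second progression a median of 5 months later. Leavers are a random sample of those who progress. They are censored at first progression, or at second progression if they crossed over. Willingness to leave is equal in both arms.

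| Null, 90% crossover | No leavers | 10% | 30% |
|---|---|---|---|
| Median OS HR | about 1.0 | 0.97 | 0.87 |
| Nominal one-sided error | 15% | about 17% | about 20% |
| Error, futility-stopped trials counted as no claim | 11% | 12% | 14% |
| Fall in the roughly 8 expected deaths | – | 0.6 | 1.8 |

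Repeat runs agree within about one percentage point. With no crossover, 30% leaving gives 16% to 17% error, which is essentially no null bias. Crossover therefore drives the shift.

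For scale, the standard error of the log hazard ratio with 8 deaths is about 2/√8 = 0.71. The shifts are ln 0.97 = −0.03 and ln 0.87 = −0.14, or about 0.04 and 0.20 of a standard error.

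**4. Which arm loses more (Model 1, 30% willing to leave).**

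| True PFS HR | Crossover | Arm A exits | Arm C exits |
|---|---|---|---|
| 1.0 | 90% | 22.7% | 12.7% |
| 0.40 | 90% | 18.4% | 17.8% |
| 0.40 | 30% | 18.5% | 23.9% |

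The order reverses because, at the design alternative, fewer Arm A patients have progressed by the analysis.

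**5. Sensitivity to who leaves (Model 2).** Here median post-progression survival is 14 months, there is a 1-month lag to joining, and longer survivors are likelier to join. With 90% crossover:
- Null, 30% joining: HR 1.00 to 1.01, error 15.7% to 14.9%.
- Null, 50% joining: HR 1.02 to 1.13, error 15.4% to 14.7%.
- PFS HR 0.40, 30% joining: OS HR 0.50 to 0.46, deaths 10.1 to 8.7.
- PFS HR 0.40, 50% joining: OS HR 0.50 to 0.43, deaths 10.0 to 7.8.

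If fitter patients are the ones who join, the null shift toward Arm A disappears. At the design alternative the hazard ratio still moves toward Arm A.

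**The case against.** The strongest reply is that OS carries little weight and the trigger is narrow. OS appears in no stated aim, and 9.4 calls it exploratory. It has no event target: with 7 or 10 deaths, Schoenfeld power at a true OS hazard ratio of 0.5 is only 45% or 52%. The exit covers COG therapeutic studies only, while the trial also enrols adults through other cooperative groups, and no follow-on COG study is named. At 10% leaving, the shift is trivial beside the noise. All of this stands, and it limits the severity. It does not remove the conflict between 8.2(c) and 9.1 or withdraw the test in 9.3.

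Two stronger readings are tempting. A reader might infer that Arm A must lose more patients because only Arm C can cross over. The documents do not support that. Crossover is optional, is limited to progression before Cycle 22 and dates from Amendment 5A. Crossed-over patients can leave at second progression, and the order of exits depends on the true PFS effect.

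A reader might also take the case where 10%, 20%, 30% or 50% of Arm A leave and nobody in Arm C does, which gives nominal errors of 17%, 19%, 21% or 29%. That case assumes no Arm C exits at all and ignores the futility stop, which ends half of null trials. Nothing in the documents supports leaving rates that high or that one-sided.

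**Conclusion.** The point holds in a limited form. Sections 8.1 and 8.2(c) contradict 9.1, and the rule makes censoring of a formally tested OS comparison plausibly informative. That it is informative is an inference from the link to recurrence; it is not documented. Neither the arm that loses more patients nor the size of the bias can be fixed from the documents, which give no OS, exit or crossover rates.

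If leavers are typical of progressed patients and crossover is common, the null OS hazard ratio falls to about 0.97 or 0.87 at 10% or 30% leaving. If leavers are fitter than average, or nobody crosses over, there is little or no null inflation. Counting futility-stopped trials as no claim, which is itself an assumption because 9.3 places the OS comparison at the final analysis, error stays at or below about 14% in the Model 1 cases shown.

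Primary PFS is largely unaffected, because an exit at recurrence normally follows the PFS event. Severity is low to moderate.

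**What to change.** Amend 8.2(c) and the matching sentence in 8.1 so that, after enrolment on another COG therapeutic study, vital status and date of death are still collected to the fifth anniversary, as 9.1 already promises. What else the exit ends, including disease assessments on this study, can stay as it is. Withdrawal of consent under 8.2(d) still stops collection.

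State in 9.4 how OS is censored if vital status cannot be obtained after such an exit. Report the number and timing of 8.2(c) exits by arm with the OS result. Say once, consistently in 9.3 and 9.4, whether OS is secondary or exploratory.

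The cost is survival-only contact, or a data link within COG, for the few patients concerned. Section 3.1.1 helps, since "The COG patient ID number is used to identify the patient in all future interactions with COG". It provides an identifier only; it does not say that another study's survival data may be shared. The link therefore needs a check of consent and data-use terms, including for anyone who has already left this way. No extra patients or study visits are needed.
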